9.5 Analysis Populations

9.5.1 Full Analysis Set

The Full Analysis Set will consist of randomized subjects that have at least one measurement on two of the periods Baha 6 Max SP, Baha 5 SP and unaided.

9.5.2 Per Protocol Population

The Per protocol population will consist of all randomized patients that have measurements on all primary and secondary variables on all three periods and have no major protocol violations.

9.6 Primary Endpoint Analyses

The first primary endpoint analysis will be the comparison of adaptive speech in noise [signal-to-noise ratio, 50% speech understanding] between the Baha 6 Max SP and unaided with two-sided Fisher's non-parametric permutation test for paired observations on significance level 0.005 on the FAS population. Mean difference with 99.5% confidence interval will be given together with the distribution of the difference.

The second primary endpoint analysis will be the comparison between Baha 6 Max SP and Baha 5 SP regarding preference of device with two-sided Sign test on significance level. Proportion of preferences for Baha 6 Max SP with exact 95 % CI will be calculated.

If one of the two primary efficacy analyses are significant but not the other, the other can be retested at the 5% significance level according to the decision rule of the Holms test (9).

9.7 Secondary Endpoint Analyses

All the secondary endpoints in section 8.2.2 will be analysed according to the statistical methods given in section 8.1 General Statistical Considerations on both the FAS population and the Per Protocol population. The two primary efficacy analyses will also be performed on the Per Protocol population

9.8 Safety Analyses

The Adverse Event will be analysed descriptively for the Safety population.

Adverse Events and Serious Adverse Events will be coded with the MeDRA dictionary and tabulated by Preferred Term-code and System Organ Class-code and treatment.

9.9 Demographics and Baseline Characteristics

Demographics and baseline characteristic will be descriptively summarised

9.10 Interim Analyses

N/A

9.11. Statistical Analysis Plan

A statistical analysis plan (SAP) with detailed statistical analyses specified for all variables will be written and signed off before the database lock.

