2 CLINICAL INVESTIGATION SYNOPSIS

Investigation title	A pivotal, prospective, single-centre, randomized test order, crossover, open label study comparing the performance of a new sound processor - Baha 6 Max with unaided hearing and Baha 5 in adult subjects with conductive or mixed hearing loss.
Short title	Baha 6 Max Home test
Investigation number	CBAS5779
Name of investigational medical device(s)	The Baha 6 Max SP
Intended use of investigational medical device(s)	
Intended use
 
The Cochlear Baha System uses bone conduction to transmit sounds to the cochlea (inner ear) with the purpose of improving hearing. The Baha 6 Max SP is intended to be used as part of the Cochlear Baha System to pick up surrounding sound and transfer it to the skull bone via a Baha Implant, Baha Softband or Baha SoundArc and can be used unilaterally or bilaterally.
 
Medical indications for use
 
The Baha System is indicated for patients with conductive hearing loss, mixed hearing loss and single sided sensorineural deafness (SSD). The Baha 6 Max SP is indicated for patients with up to 55 dB SNHL.
 
The regulatory status is pre-market.

Name and description of comparator device/product(s)	
The comparator will be the Baha 5 SP.
 
Intended use
 
The Cochlear Baha System uses bone conduction to transmit sounds to the cochlea (inner ear) with the purpose of improving hearing. The Baha 5 SP is intended to be used as part of the Cochlear Baha System to pick up surrounding sound and transfer it to the skull bone via a Baha Implant, Baha Softband or Baha SoundArc and can be used unilaterally or bilaterally.

	
Medical indications for use
 
The Baha System is indicated for patients with conductive hearing loss, mixed hearing loss and single sided sensorineural deafness (SSD). The Baha 5 SP is indicated for patients with up to 45dB SNHL.
 
The Baha 5 SP is a CE marked medical device.

Expected start date (first subject consented)	The start of the study has been delayed due to Covid-19 pandemic. New estimated start date beginning of September 2020.
Expected enrolment period	6 weeks
Expected duration per subject	14 days +/- 4 days
Expected total duration of the clinical investigation	8 weeks
Number of subjects planned	16
Number of investigational sites planned	One site

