7 DESIGN OF THE CLINICAL INVESTIGATION

7.1 General

[figure not shown]

Figure 4. Schematic for the investigation

This investigation is a pivotal, prospective, single-centre, randomized test order, cross-over, open label investigation comparing the performance of a new SP - Baha 6 Max SP with unaided hearing and Baha 5 SP in adult subjects with conductive or mixed hearing loss.

The evaluation of sound quality and listening effort through sound clips at visit 3 will be performed single-blinded, i.e. the test subject will not know if Baha 6 Max SP or Baha 5 SP is connected to the abutment.

The subjects include men and women aged 18 or older who are currently using the Baha Connect System (percutaneous Baha). Subjects will be screened, and 16 eligible subjects will be enrolled in the clinical investigation. Eligible subjects will be randomly assigned to one of two investigational arms using a 1:1 randomisation ratio. Subjects will be randomised either to first test the Baha 6 Max SP and thereafter Baha 5 SP or Baha 5 SP followed by Baha 6 Max SP.

After signing the informed consent, subjects will attend scheduled study visits over a three-week period to be assessed as described in the CIP Schedule of Events (Section 3). At study visits, subjects will undergo hearing assessments and safety assessments.

The first primary endpoint is to determine the hearing performance of Baha 6 Max SP in comparison with unaided hearing and the second primary endpoint is the comparison of preference between the devices. The second primary objective is to compare the hearing performance between Baha 6 Max SP and Baha 5 SP when it comes to subject preference.

Safety will be assessed by recording and summarising all AEs/ADEs and DDs. All subjects will attend an End-of-Study visit at the time they complete the investigation.

No data monitoring committee will be used for this clinical investigation.

After the investigation a subject will continue to use the SP currently prescribed to him/her.

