7.2.6 Criteria for Subject Withdrawal

Subjects can decide to withdraw from the investigation at any time. The Investigator shall ask the reason(s). The reason for withdrawal should be documented in the subject's source files and the case report form (CRF).

The Investigator or Sponsor may also decide to withdraw a subject from the clinical investigation if it is considered to be in their best interests.

Subject withdrawal may be for any of the following reasons:

- Adverse Event (AE)
- Device Deficiency (DD)

- CIP or GCP deviation
- Subject lost to follow-up
- Subject withdrew consent
- Subject death
- Sponsor decision
- Investigator decision
- Other (specify)

If subject withdrawal is due to problems related to the IMD or comparator safety or performance, the Investigator shall ask for the subject's permission to continue in safety follow up (i.e., adverse events) until their scheduled End-of-Study visit.

If a subject is lost to follow-up, every possible effort must be made by the study site personnel to contact the subject and determine the reason for discontinuation. At least 3 separate attempts taken to contact the subject must be documented.

Enrolled subjects who are withdrawn/discontinued will not be replaced. Randomisation Procedures

The test order between the two SPs will be randomised based on a computer-generated randomisation schedule prepared by the Sponsor.

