7.6 Sponsor Role in Conduct of the Clinical Investigation

The investigation will be conducted by audiologist employed by CBAS and the investigation will be conducted at CBAS facilities.

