4.2 Analyses

4.2.1 Pass/Fail Criteria

If the signal-to-noise-ratio for a subject is at least 50% regarding speech understanding the subject will be classified as a responder. The primary objective of the study is that the null-hypothesis that the proportion of responders for the Baha 6 Max SP and the Baha 5 SP are equal.

If the two-sided p-value when testing the hypothesis above is below 5% the results of the study are considered successful.

This means that the pass/fail criteria for each subject is speech understanding and the pass-criteria is that the signal-to-noise-ratio for a subject is at least 50%.

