6 CHANGE HISTORY

Version	Change	Author	Date
1.0	Original SAP from StatCons released 22-Oct-2020. This version is an integration into Cochlear SAP template.	[REDACTED]	3-Mar-2021

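### The SAP need only be signed before database lock in an open-label, sponsor-run trial, nothing says the protocol prevails over it, and the SAP on file replaces the first primary analysis

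*Protocol*

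**What the plan says.** **Timing.** Protocol 9.11 holds the only rule on when the SAP is finalised: it "will be written and signed off before the database lock". Nothing ties sign-off to the first subject, the first outcome or access to data.

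**Conduct.** Section 7.1 describes a "randomized test order, cross-over, open label investigation". Only the sound-clip rating, a secondary endpoint, is blinded, and only to the subject. Section 7.6 states: "The investigation will be conducted by audiologist employed by CBAS and the investigation will be conducted at CBAS facilities". The test order comes from a "computer-generated randomisation schedule prepared by the Sponsor" (text under 7.2.6).

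**Confirmatory analyses in the protocol.** Section 9.6 compares SNR "between the Baha 6 Max SP and unaided with two-sided Fisher's non-parametric permutation test for paired observations on significance level 0.005". Preference is tested by a Sign test at 0.045 (9.1, 9.3.1). If one test is significant, the other may be retested at 5% (9.6). Section 9.1 claims a total type I error below 0.05 and gives confirmatory weight to these two p-values only. Section 18 requires changes to the protocol to be documented as an amendment.

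**The SAP.** Sections 4.2.1 and 4.2.2 define a responder from the speech-in-noise test, compare responder proportions between Baha 6 Max and Baha 5 with a Binomial test, and add: "If the two-sided p-value when testing the hypothesis above is below 5% the results of the study are considered successful". SAP section 1 promises to report deviations from the SAP. It is silent on deviations of the SAP from the protocol.

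**Dates.** SAP section 6 records: "Original SAP from StatCons released 22-Oct-2020". The version on file is dated 3-Mar-2021 and described as a move into the sponsor's template. The protocol synopsis gives: "New estimated start date beginning of September 2020".

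**The concern.** Signing a SAP before lock protects a trial when results by treatment stay hidden until lock. Here the staff who run the tests are the sponsor's employees and know which device is being worn. With 16 subjects, the direction of preference can be seen by counting.

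The type I error claim in 9.1 depends on comparison, endpoint, test and level being fixed in advance. The protocol does fix them. The weakness is that a later document can state something else with no rule on which text governs, and here it does. If the SAP were followed as written, success would be decided on a comparison with Baha 5 and not on the comparison with unaided hearing, which section 7.1.1 says is intended to support regulatory approval.

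**Working it through.** **1. The protocol's own figures (9.4) reproduce.**
- First primary: mean difference 16 dB, SD 12.5, n = 15, two-sided alpha 0.005. The standardised effect is 16/12.5 = 1.28 and the noncentrality is 1.28 × √15 = 4.96. Paired noncentral-t power is 92.4%; a simulated sign-flip permutation test gives 90.9%. At n = 14 these are 89.2% and 87.8%. So 15 subjects for 90% power holds.
- Second primary: n = 16, 86% preferring Baha 6 Max, alpha 0.045. The test rejects at 13 or more of 16, with two-sided size 2 × (560 + 120 + 16 + 1)/65536 = 0.0213. Exact power is 82.4%, so at least 80% holds.
- Alpha: 0.005 + 0.045 = 0.05.

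**2. First primary analysis side by side.**

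| | Protocol 9.1, 9.3.1, 9.6 | SAP 4.2.1, 4.2.2 |
|---|---|---|
| Comparator | Unaided | Baha 5 |
| Endpoint | SNR in dB, continuous | Responder, yes/no |
| Test | Paired permutation | Binomial |
| Level | 0.005 | 0.05 |
| Multiplicity | 0.005/0.045 split, Holm-type retest | Not stated |

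SAP 4.1 still quotes the unaided comparison at 0.0050, so the SAP also disagrees with itself. The protocol's change history lists no change to section 9. The SAP is based on protocol version 3.0; version 4.0 changed only section 8.4, so the version gap does not explain the difference.

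**3. Effect on the level.** 0.05/0.005 = 10, on a different comparison. The preference test is barely affected: a Sign test is a binomial test at 0.5, and at n = 16 without ties the rejection count is 13 at either 0.045 or 0.05. What is lost there is the explicit level and the retest rule.

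**4. Effect on power.** The 90% figure belongs to a continuous comparison with unaided hearing. Suppose a usable responder cut-off existed and the Binomial test were exact on discordant pairs. Five of five in one direction gives p = 2 × 0.5^5 = 0.0625; six of six gives 2 × 0.5^6 = 0.031. At least 6 discordant subjects of 16 are therefore needed. If every discordant subject favoured Baha 6 Max, power would be P(M ≥ 6) with M ~ Binomial(16, d):

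| Assumed discordance d | 10% | 20% | 30% | 40% | 50% |
|---|---|---|---|---|---|
| Power | 0.3% | 8% | 34% | 67% | 89% |

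The documents give no discordance rate. Nor is the responder rule usable as written: the adaptive test (protocol 7.3.3) holds understanding at 50% and returns a dB value, so an SNR of at least 50% does not separate subjects.

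**5. Calendar, on planned dates only.** A start between 1 and 10 September 2020 plus 8 to 9 weeks puts the last visit between about 27 October and 12 November 2020. The SAP of 22-Oct-2020 then falls 42 to 51 days after the start. With even enrolment over 42 days and 14 days per subject, between 16 × 28/42 ≈ 11 and 16 × 37/42 ≈ 14 subjects would have finished Visit 3. The version of 3-Mar-2021 falls about 16 to 18 weeks after the planned last visit. Actual first-visit, last-visit and lock dates are not given.

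**The case against.** The strongest reply is that 9.11 is not the cause. Sign-off before lock is common practice. Sections 9.1, 9.3.1 and 9.6 already fix the confirmatory analyses, 9.11 asks the SAP only for detail, and section 18 requires an amendment for any protocol change. A SAP signed before randomisation could have carried the same text.

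Much of this stands. Section 9.11 does not itself permit the swap, and an earlier date alone would not have prevented it. What remains is that section 18 does not mention the SAP, no passage ranks the two documents, and the SAP departs from section 9 with no amendment and no stated reason.

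A second reply is that access to the data is controlled. Section 14 provides role-based permissions, no interim analysis is planned, and the analyst's identity is redacted, so independence cannot be judged. This is fair as far as the SAP author goes: nothing shows that person saw results. It does not alter the fact that sponsor-employed testing staff see outcomes by device.

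A reader might infer from the dates that the analysis was changed after results were known. The documents do not support that. The March 2021 version is described as a template integration, the October 2020 version falls before the planned last visit, and nothing shows which of them introduced the responder hypothesis. The unusable cut-off looks as much like a drafting error as a choice driven by results.

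**Conclusion.** The point holds as a gap in governance with a visible consequence. The only SAP deadline is one that protects little in this design, no sentence gives the protocol precedence, and the SAP on file decides success on a different comparison, endpoint and test at ten times the nominal level. The error claim in 9.1 and the 90% power in 9.4 do not describe that test.

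A reader might go further and add the SAP's 5% to the protocol's levels, 0.005 + 0.045 + 0.05 = 0.10, and report that as the true error rate. That needs a rule under which any of three tests suffices. Neither document states one; the SAP replaces the first primary and ties success to that single hypothesis. An exact binomial test with at most 16 discordant pairs would also have size of at most 20/512 = 0.039, not 0.05. Because the responder rule is not usable as written, no specific inflated rate can be derived.

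The conclusion rests on the text of the two documents and not on the calendar, which uses planned dates.

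**What to change.** 1. Add to protocol 9.11 and to the SAP: the confirmatory comparisons, endpoints, tests and levels are those of protocol 9.1, 9.3.1 and 9.6, namely SNR against unaided at 0.005, preference against Baha 5 by Sign test at 0.045, and the Holm-type retest. The SAP may add detail but may not replace them. Any departure is dated and reported as post hoc.
2. Rewrite SAP 4.2.1 and 4.2.2 to match; a precedence sentence alone would leave them contradicting it. In protocol 9.3.1, correct the preference sentence, which names unaided as the comparator where the hypotheses below it name Baha 5. In 9.6, insert the missing 0.045 for the preference test.
3. If still possible, sign the SAP before the first outcome is measured. Otherwise state who had access to outcome data at the time of each SAP version.

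The cost is a short protocol amendment under section 18, with the ethics steps that follow from it, a revised SAP, and earlier SAP drafting. No extra subjects, visits or data are needed.

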10 INFORMED CONSENT PROCESS

The Investigator shall obtain written informed consent from the subject using an approved ICF prior to any clinical investigation-related examination or activity. The rationale of the clinical investigation, as well as the risks and benefits, what participation will involve, and alternatives to participation will be explained to the subject. Ample time will be provided for the subject to enquire about details of the clinical investigation and to decide whether to participate.

All questions about the clinical investigation shall be answered to the satisfaction of the subject or the subject's legally acceptable representative. Subjects shall not be coerced or unduly influenced to participate or to continue to participate in a clinical investigation.

Each subject and the person who conducted the informed consent discussion, shall sign and date the Informed Consent Form (ICF). A copy of the signed ICF shall be given to the subject. The original signed ICF shall be archived in the Investigator's Site File or subject file at the investigational site.

The subject shall be informed in a timely manner if new information becomes available that may be relevant to the subject's willingness to continue participation in the clinical investigation. The communication of this information must be documented as an update to the ICF and re-consent of the subject.

11 ADVERSE EVENTS AND DEVICE DEFICIENCIES

11.1 Definitions

11.1.1 Adverse Event

An adverse event (AE) is any untoward medical occurrence, unintended disease or injury, or untoward clinical signs (including abnormal laboratory findings) in subjects, users or other persons whether or not related to the medical device or the procedures required for implant or use.

NOTE 1: This definition includes events related to the medical device or the comparator device.

NOTE 2: This definition includes events related to the procedures involved.

NOTE 3: For users and other persons, this definition is restricted to events related to medical devices.

11.1.2 Adverse Device Effect

An adverse device effect (ADE) is an AE related to the use of a medical device.

NOTE 1: This includes any AE resulting from insufficiencies or inadequacies in the instructions for use, the deployment, the implantation, the installation, the operation, or any malfunction of the medical device.

NOTE 2: This definition includes any event resulting from use error or from intentional misuse of the medical device.

11.1.3 Serious Adverse Event

A serious adverse event (SAE) is any AE that:

- a) led to a death,
- b) led to a serious deterioration in the health of the subject that either resulted in:
 - a life-threatening illness or injury, or
 - a permanent impairment of, or damage to, a body structure or a body function, or
 - in-patient hospitalisation or prolonged hospitalisation, or
 - medical or surgical intervention to prevent life-threatening illness or injury or permanent impairment or damage to a body structure or a body function, or
 - Chronic disease.
- c) led to foetal distress, foetal death or a congenital physical or mental abnormality, or birth defect

NOTE: Planned hospitalisation for a pre-existing condition, or a procedure required by the CIP, without serious deterioration in health, is not considered a SAE.

11.1.4 Serious Adverse Device Effect

A serious adverse device effect (SADE) is an ADE that has resulted in any of the consequences characteristic of a SAE.

11.1.5 Unanticipated Serious Adverse Device Effect

An unanticipated serious adverse device effect (USADE) is a SADE, which by its nature, incidence, severity, or outcome has not been identified in the current version of the Investigator's Brochure

NOTE: An anticipated serious adverse device effect is an effect, which by its nature, incidence, severity, or outcome has been identified in the Investigator's Brochure.

11.1.6 Adverse Events of Special Interest

N/A

11.1.7 Device Deficiency

A Device Deficiency (DD) is an inadequacy of a medical device with respect to its identity, quality, durability, reliability, safety, or performance.

NOTE: Device Deficiencies include malfunctions, use errors, and inadequate labelling or information supplied by the manufacturer.

11.2 Recording and Handling of Adverse Events

Subjects shall be carefully monitored during the clinical investigation and the investigator should enquire about AEs at investigation visits.

AEs will be recorded from the time of first use/contact with the IMD and/or comparator. AE recording will continue for each subject until completion of their End of Study visit. Ongoing SAEs and SADEs will be followed for 30 days, or until resolution or stabilisation of the event, whichever comes first.

Source notes should indicate the evaluation for AEs, even if none to report. All required AEs will be reported if observed, even if anticipated and/or acknowledged as a risk factor in the consent.

All AEs will have the following information documented: start and stop dates, action taken, outcome, severity and investigators opinion on the potential relationship to the IMD and/or comparator and study procedures. If an AE changes in severity, the most severe (highest) grade will be captured for that event on the Adverse Events CRF.

11.2.1 Assessment of Severity

The Principal Investigator (or qualified delegate) will make an assessment of severity for each event based on clinical judgement. The intensity of each event recorded in the CRF should be assigned to one of the following categories:

Table 3. Intensity of event.

Mild	An event that is easily tolerated by the subject, causing minimal discomfort and not interfering with everyday activities.
Moderate	An event that is sufficiently discomforting to interfere with normal activities
Severe	An event which is incapacitating and prevents normal everyday activities

